### **10.1 Analysis populations**

Three analysis sets will be defined:

1) A Full Analysis Set (FAS) which will include all randomized patients who provided informed consent or died during the index procedure. Patients will be analyzed according to the intention-to-treat (ITT) principle, that is, in the group to which they were randomized.

2) A Per Protocol set (PPS) which will all patients who were randomized, provided informed consent or died during the index procedure and had no major protocol violations. Patients will be analyzed according to the intention-to-treat (ITT) principle, that is, in the group to which they were randomized.

In a blinded to outcome review meeting just before the interim analysis for efficacy and the final data base lock, it will be determined which patients will be excluded from the PP set. All major protocol deviations that lead to exclusion from the PP set will be fully documented in the Analysis Sets Specification Document that will be dated and signed prior to database lock.

3) A safety set (SS) which will include all randomized patients. Patients will be analyzed in the group based on which treatment they actually received. In case a patient did not receive a stent, the patient will be analyzed in the group to which the patient was randomized.

The primary and secondary endpoints will be analysed for the FAS and PPS. Safety endpoints will be analysed for the 3 populations.

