## **10. STATISTICAL ANALYSIS**

The statistical analysis and reporting of the trial will be in accordance with the CONSORT guidelines. Baseline data will be reported by treatment allocation as categorical or continuous variables, where appropriate. Missing baseline data will be imputed using regression imputation. For the primary endpoint, statistical analyses will be performed according to the per-protocol (PP) principle as well as the intention to treat (ITT) principle. Both PP and ITT analyses must demonstrate non-inferiority in order to conclude that immediate CAS during EVT is non-inferior to a deferred treatment strategy.

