### 11.2 Recruitment and consent

This trial will include patients using a deferred written informed consent procedure. This means that, after the treatment, written informed consent is obtained by asking the patient, or a legal representative of the patient. The justification for the deferred consent is as follows. Firstly, during acute ischemic stroke, the adagium “time is brain” holds. Reperfusion therapy should be initiated as soon as possible. For every hour delay, the chance of recovery to activities of daily living (ADL) independency decreases with 6%. It has been observed in previous acute stroke trials, that obtaining informed consent before start of the treatment, led to an (unacceptable) delay in treatment onset. Secondly, during the acute phase of acute ischemic stroke a patient is often unable to make a well thought out decision on whether to participate in a study, due to neurological deficits like language disturbances, unable to communicate or anosognosia (unaware of his or her medical condition). Obtaining consent from the patient’s proxy will also unacceptably delay the EVT itself. In summary due to the emergency situation as well as the lack of decision-making capacity, the trial cannot be performed without a deferred consent approach. This approach has been successfully used in recent acute stroke trials in the Netherlands.

After treatment, informed consent will be obtained by asking the patient or a legal representative of the patient, preferably within 24 hours after EVT. The patient and/or representative will be provided with a verbal and written explanation of the study by the local investigator. They will be asked for consent to use their data, biomaterials for the purpose of the study and to perform follow up investigations. Participation in the study is voluntary and at any given time, informed consent can be withdrawn. If the patient has died before informed consent has been obtained, the patient’s proxy’s will be informed about the study, the treatment the patient has received and the use of the data that has been collected. Because mortality is an important safety endpoint, data of these patients will be (anonymously) stored, in order to provide these data to the DSMB.

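### Patients who die after the procedure but before deferred consent fall outside both the full analysis set and the per-protocol set, so some mRS 6 outcomes are lost from both decisive analyses

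*Protocol*

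**What the plan says.** All references are to the protocol.

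- **Analysis sets (10.1).** The full analysis set (FAS) holds "all randomized patients who provided informed consent or died during the index procedure". The per-protocol set (PPS) holds randomised patients who "provided informed consent or died during the index procedure and had no major protocol violations". The third set has no consent filter: "A safety set (SS) which will include all randomized patients".
- **Use of the sets (10.1 and the opening of 10).** "The primary and secondary endpoints will be analysed for the FAS and PPS". For the conclusion, "Both PP and ITT analyses must demonstrate non-inferiority".
- **Timing of consent (11.2).** Consent is asked of the patient or a legal representative after treatment, "preferably within 24 hours after EVT". No latest time is given.
- **Death before consent (11.2).** This case is foreseen: "If the patient has died before informed consent has been obtained", the relatives are informed, and "data of these patients will be (anonymously) stored, in order to provide these data to the DSMB". No step brings these patients into the FAS or PPS.
- **Related rules.** Death is level 6 of the primary outcome (8.1.1). Mortality at 90 days is a secondary endpoint (8.1.2). Data of patients who decline consent are kept out of the primary endpoint (8.4). Each patient without consent is replaced (8.5).

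**The concern.** Membership of the FAS is decided after randomisation and partly by the outcome itself. A death on the angiography table counts as mRS 6. A death some hours later counts only if somebody has already consented. The protocol gives no reason for drawing the line at the end of the procedure, and by keeping procedural deaths it already accepts using data of some deceased patients without consent.

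Two features raise the stakes:

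- Requiring non-inferiority in both the ITT and the per-protocol analysis normally guards against a weakness in one of them. Here both sets carry the same filter, so neither can correct the other.
- The formal analysis of 90-day mortality, as a secondary endpoint, uses the same two sets and loses the same deaths.

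If these deaths are unevenly distributed between the arms, the common odds ratio (cOR) moves in favour of the arm that loses more of them.

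**Working it through.** **Does the gap exist?** Take a patient who dies on the ward before anyone has consented.

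1. First FAS condition (consent given): not met.
2. Second FAS condition (death during the index procedure): not met.
3. The PPS uses the same two conditions, so the patient is not in it either.
4. Section 11.2 stores the data for the DSMB and names no other use.
5. The safety set includes the patient.

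The gap follows from the wording alone.

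**How large could the effect be?** The protocol gives no figure for deaths in this window, so there is none to reproduce. The rates below are assumptions.

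Inputs from 4.5:
- deferred-arm mRS 0 to 6: 6.9, 20.2, 17.9, 16.4, 17.2, 8.0, 13.4%
- margin cOR 0.80
- two-sided alpha 0.05, that is 2.5% on the non-inferiority side
- 300 per arm

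Step 1. Place the stenting arm exactly at the margin by multiplying each cumulative odds of the deferred arm by 0.80. For death: the deferred odds of mRS 0 to 5 are 0.866/0.134 = 6.463; times 0.80 = 5.170; the probability is 5.170/6.170 = 0.838. So mRS 6 is 16.2% in the stenting arm (48.6 of 300) against 13.4% in the deferred arm (40.2 of 300).

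Step 2. Remove the assumed pre-consent deaths from the mRS 6 cell and refit the unadjusted proportional odds model to the expected counts. For example, removing 2% from the stenting arm leaves 42.6 deaths among 294 patients.

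Step 3. Chance of falsely declaring non-inferiority = Φ( ln(cOR/0.80)/SE − 1.96 ), with SE of the log cOR about 0.145 from the fit. With no removal this is Φ(−1.96) = 2.5%.

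| Removed, stenting / deferred | Patients | Fitted cOR | ln(cOR/0.80) | False non-inferiority |
|---|---|---|---|---|
| 0 / 0 | 0 / 0 | 0.800 | 0 | 2.5% |
| 1% / 0 | 3 / 0 | 0.820 | 0.025 | 3.7% |
| 2% / 0 | 6 / 0 | 0.841 | 0.050 | 5.3% |
| 3% / 1% | 9 / 3 | 0.839 | 0.047 | 5.1% |
| 2% / 2% | 6 / 6 | 0.794 | −0.008 | 2.2% |
| 0 / 1% | 0 / 3 | 0.778 | −0.028 | 1.6% |
| 0 / 2% | 0 / 6 | 0.755 | −0.058 | 0.9% |

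Worked line for 2% / 0: 0.050/0.145 = 0.345; Φ(0.345 − 1.96) = Φ(−1.615) = 5.3%.

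The rows 2% / 0 and 3% / 1% nearly agree, so the net difference between arms drives the result, not the total number removed. A net excess of six patients in the stenting arm roughly doubles the nominal error. The same excess in the deferred arm makes the test conservative.

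**The case against.** The strongest reply concerns direction and reach, not the text.

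- **Direction.** A reader might infer that the gap favours stenting, because antiplatelet treatment and hyperperfusion could cause early haemorrhage. The protocol does not establish this. Section 13.2 expects a risk of intracranial haemorrhage that is comparable to slightly higher with stenting. Section 12.2 describes symptomatic haemorrhage as similar between the groups in earlier cohorts, and 13.1 says most studies found no increase. The only mortality figures (4.5, observational, 90 days) are lower with stenting: 11.4% against 13.4%. If pre-consent deaths followed that pattern, the bias would work against stenting. This objection stands.
- **Hidden harm.** A reader might also infer that deaths from stenting would go unseen. They would not. The safety set holds every randomised patient, and the DSMB receives deaths before consent and must review safety after every 10 deaths and every 5 symptomatic haemorrhages (9.5). This stands too, but neither the safety set nor the DSMB data decide non-inferiority.
- **Reach.** A representative can consent within the first day, so many early deaths will already be in the FAS as mRS 6. Only deaths between the end of the procedure and consent are lost. This stands, and it is why rates of 1% to 2% can only be assumptions.
- **Feasibility.** Storage is described as anonymous and for the DSMB. The text does not say that allocation and the model covariates of 10.2 are kept in a form usable for the primary analysis. This stands and shapes the remedy.

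It is no answer that the statistical analysis plan might repair the sets, since the protocol itself fixes them.

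**Conclusion.** The gap is real on the protocol's wording. Deaths after the index procedure and before deferred consent are left out of both analyses that must show non-inferiority, and out of the analysis of 90-day mortality as a secondary endpoint. They remain in the safety set and in the DSMB's view.

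The size and sign of the bias are open. At a true cOR of 0.80, false non-inferiority runs from 0.9% (2% excess in the deferred arm), through 2.2% (2% in each arm), to 5.3% (2% excess in the stenting arm), against a nominal 2.5%. These figures rest on assumed rates, 300 per arm and an unadjusted model. A claim that the plan is biased towards stenting would go further than the documents allow.

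This should be fixed, because the imbalance cannot be known in advance and the rule can be settled before outcomes by arm are seen. Confidence is high for the gap in the text and moderate for the size and direction of the bias.

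**What to change.** 1. **Section 10.1.** Define the FAS and PPS to include randomised patients who died before consent could be obtained, at any time after randomisation, scored mRS 6. The PPS keeps its exclusion for major protocol violations. Exclude for lack of consent only patients who, themselves or through a representative, actively refused (in line with 8.4), and report refusals by arm.
2. **Section 11.2.** With ethics committee agreement, state that allocation, death and the covariates of the primary model are retained for these patients and may be used in the primary analysis. Impute missing covariates; section 10 already plans imputation of missing baseline data.
3. **Section 8.5.** State that replacing a patient without consent does not remove a patient who died before consent from the analysis.
4. **Fallback.** If the ethics committee does not allow full inclusion, prespecify a sensitivity analysis of the primary endpoint that counts these deaths as mRS 6 by arm.

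The cost is an amendment to three sections and an ethics decision on using data of deceased patients without consent. That decision is a real step, not only wording. The planned sample size of 600 does not change.

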For the sample size calculation, we used data from the Dutch MR CLEAN registry, a nationwide cohort of EVT treated patients between 2014-2018. Based on the mRS distributions in the immediate CAS group (mRS 0: 17.9%, mRS 1: 22.3%, mRS 2: 16.7%, mRS 3: 14.4%, mRS 4: 12.3%, mRS 5: 5.0%, mRS 6: 11.4%) and in the deferred treatment group (mRS 0: 6.9%, mRS 1: 20.2%, mRS 2: 17.9%, mRS 3: 16.4%, mRS 4: 17.2%, mRS 5: 8.0%, mRS 6: 13.4%), we calculated the assumed effect size to be a common odds ratio (cOR) of 1.15 for a shift in favorable direction on the full mRS. The non-inferiority margin was set to a cOR of 0.8, corresponding to an absolute difference of approximately 5% in favorable outcome (mRS 0-2). This is a generally accepted margin in the stroke research community and has been recently used in comparable EVT trials. We used Monte Carlo simulations with 5000 runs to calculate the required sample size based on the assumptions above showing that a sample size of 610 patients, would provide 80% power (at a two-sided alpha level of 0.05) to determine that the lower bound of the cOR 95% confidence interval (CI) does not cross the non-inferiority margin of 0.8. Covariate adjustment for major prognostic variables that included age, pre-stroke mRS score, stroke severity, collateral score and time from symptom onset to randomization results in a reduction of at least 15% in the required sample size (n=520). Assuming a crossover rate of 3% in each arm (6% for both groups), necessitates an increase in sample size by factor  $1/(1 - \% \text{ crossover})^2 = 1/(1 - 0.06)^2 = 1.13$ . So taking crossovers into account, the sample size increases to 588 (520\*1.13). Based on the experience of the MR CLEAN NO-IV trial and MR CLEAN-MED trial, the number of patients lost to follow up is expected to be low

(0 in both recently completed trials). Assuming a combined percentage of 2% due to loss to follow up and to erroneous inclusions (for example inclusion of patients who appear to have carotid dissection or carotid pseudo-occlusion) the sample size will need to be increased to a total sample size of 600 patients (n= 300 per group).

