### **8.4 Withdrawal of individual subjects**

Subjects can leave the study at any time for any reason if they wish to do so without any consequences. The investigator can decide to withdraw a subject from the study for urgent medical reasons. Data from patients who waive consent will not be used for the primary endpoint of the study, but their data will be used in a strictly anonymized form to obtain data for the purpose of safety analysis to accurately describe the group without consent.

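### The only set holding every randomized patient, the safety set, is regrouped in one direction only, so patients outside the FAS never enter an as-randomized safety comparison

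*Protocol*

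**What the plan says.** Protocol section 10.1 defines three analysis sets.

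- **FAS:** "A Full Analysis Set (FAS) which will include all randomized patients who provided informed consent or died during the index procedure". It is analysed by randomized group.
- **PPS:** patients who "provided informed consent or died during the index procedure and had no major protocol violations". It is also analysed by randomized group.
- **Safety set:** "A safety set (SS) which will include all randomized patients". The grouping rule is "Patients will be analyzed in the group based on which treatment they actually received", followed by the exception "In case a patient did not receive a stent, the patient will be analyzed in the group to which the patient was randomized".

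The section closes with "Safety endpoints will be analysed for the 3 populations".

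Three other sections show that safety data exist for people outside the FAS. Section 8.4 says of patients who waive consent that "their data will be used in a strictly anonymized form to obtain data for the purpose of safety analysis". Section 8.6 commits to registering at least serious adverse events, intracerebral hemorrhage and mortality for those who do not consent. Section 11.2 keeps the data of patients who die before consent is obtained, because mortality is an important safety endpoint.

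**The concern.** The two sentences on the safety set do not treat crossovers alike. For a control stented during thrombectomy, the first sentence applies and the patient is counted under immediate stenting. For a patient allocated to stenting who left the angiography suite without a stent, the exception applies and the patient is again counted under immediate stenting. Section 5.1 describes the control procedure as thrombectomy without stenting, so this second patient is not grouped by the procedure received. Crossovers of both kinds end in one group. The result is neither an as-randomized nor an as-treated comparison, and the protocol gives no reason for it.

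This would matter little if the same patients were also compared as randomized elsewhere, but for one subset they are not. Consent is deferred, and FAS membership depends on consent or on death during the index procedure. A patient who dies the next day from hemorrhage, before consent, is outside the FAS as worded. So is a patient who survives and refuses. Comparing safety is the trial's secondary objective (section 2), and early deaths before consent are exactly where a fatal hemorrhage would be found.

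A smaller point of wording: the exception refers to a stent without saying when it was placed, although controls may receive a deferred stent as part of their allocated strategy.

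**Working it through.** **1. Group sizes.** Section 4.5 gives the only crossover figure, 3% in each arm. The plan's chain reproduces: 520 × 1.13 = 587.6, stated as 588; 588 / 0.98 = 600, or 300 per group. Crossovers per arm: 0.03 × 300 = 9.

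| Grouping | Immediate stenting | Deferred |
|---|---|---|
| As randomized | 300 | 300 |
| Safety-set rule | 300 + 9 = 309 | 300 − 9 = 291 |
| Symmetric as-treated | 300 − 9 + 9 = 300 | 300 − 9 + 9 = 300 |

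Section 8.5 replaces each patient without consent, so the real safety set will exceed 600 by a number the protocol does not give. The 300 per arm is illustrative.

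**2. Who is only in the safety set.**

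| Patient | FAS | PPS | Safety set |
|---|---|---|---|
| Consented | yes | yes, if no major violation | yes |
| Died during index procedure | yes | yes, if no major violation | yes |
| Died after the procedure, before consent | no | no | yes |
| Survived, refused consent | no | no | yes |

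The last two rows have no as-randomized safety comparison. The protocol gives no refusal rate or rate of death before consent, so their number cannot be calculated.

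**3. Size if crossovers carry ordinary risk.** Assume hemorrhage risk of 8% when stented and 6% when not, within the 5–10% quoted in section 12.2.

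- As randomized: (291 × 0.08 + 9 × 0.06)/300 − (291 × 0.06 + 9 × 0.08)/300 = 7.94% − 6.06% = 1.88 points.
- Safety-set rule: (291 × 0.08 + 9 × 0.06 + 9 × 0.08)/309 − 0.06 = 7.94% − 6.00% = 1.94 points.
- Symmetric as-treated: 8.00% − 6.00% = 2.00 points.

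The rule falls between the other two, and the differences are negligible.

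**4. Size if crossed-over controls are at high risk.** Assume no effect of stenting, 7.5% overall in each arm (the midpoint of 5–10%), and risk *r* in the 9 stented controls. Neither the documents nor any figure in them supports a value for *r*; 15% and 25% are assumptions.

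Difference = (22.5 + 9*r*)/309 − (22.5 − 9*r*)/291

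- *r* = 0.15: 23.85/309 − 21.15/291 = 7.72% − 7.27% = 0.45 points.
- *r* = 0.25: 24.75/309 − 20.25/291 = 8.01% − 6.96% = 1.05 points.

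The as-randomized difference is zero by construction.

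**5. What symmetry can and cannot do.** If crossovers of both kinds have 20% risk and everyone else 7%, both the as-randomized and the symmetric as-treated difference are zero. The rule gives (291 × 0.07 + 18 × 0.20)/309 − 0.07 = 0.76 points. In step 4, however, symmetry does not help. Moving 9 unstented patients at the ordinary 7.5% to control gives a difference of 2 × 9 × (*r* − 0.075)/300, again 0.45 and 1.05 points. Only the as-randomized comparison is free of the distortion in both cases.

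**The case against.** The strongest reply is that section 10.1 already plans as-randomized safety analyses in the FAS and PPS, so a distortion from regrouping would show when the FAS and safety set are compared. The first half stands in full. A reader might infer from the grouping rule that the trial has no as-randomized safety comparison at all, and that is wrong. The second half stands only in part. The FAS and safety set differ in membership as well as grouping, so a difference between them could not be attributed to either.

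The rule can also be defended as cautious. Counting every patient stented during thrombectomy as exposed does not hide harm from stenting, and in the assumed high-risk scenarios the shift runs against the experimental arm. An unstented patient in the stenting arm may also have had intravenous aspirin beforehand (section 5.2), so has not purely received the control treatment. This is reasonable, but the protocol does not say it, and it supports the rule as an additional analysis, not as the only grouping of all randomized patients.

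The magnitude is fairly challenged. Nothing in the protocol says that controls cross over because their procedure went badly, and no crossover rate above 3% is stated. The standard error of a risk difference at 7.5% with 300 per arm is √(2 × 0.075 × 0.925/300) = 2.2 points, so even the upper figure of 1.05 is about half a standard error.

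A reader might also infer that the DSMB's monitoring of hemorrhage and death is biased. The documents do not support that. Section 8.2 has the independent statistician combine treatment allocation with the clinical data for the DSMB, which points to the allocated group, and section 9.5 does not tie DSMB reviews to the safety-set rule.

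Finally, a reader might take the wording on stents to mean that a control with a deferred stent is counted under immediate stenting. The more natural reading is that such a patient received the control strategy and stays in control. The text should say so, but this is a clarification and not an error.

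**Conclusion.** The point holds in a limited form. As worded, the safety set places crossovers of both kinds in the immediate-stenting group (309 versus 291 at 3% crossover per arm), and it is the only set containing refusers and patients who die after the procedure but before consent. For those patients no as-randomized safety comparison is planned, although their safety data are kept.

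The group sizes follow from the text and the stated 3%. The bias does not. At 3% it ranges from negligible, with ordinary-risk crossovers, to about 0.5–1.1 points against stenting, if crossed-over controls carry an assumed 15–25% risk. These figures measure the grouping rule; the effect of the patients missing from the FAS cannot be quantified from the protocol. The primary analysis is unaffected, and no effect on DSMB monitoring is shown. This is a free improvement, not a flaw that threatens the trial's conclusions.

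**What to change.** In section 10.1:

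1. State that the safety set (all randomized patients, for the safety data held) is analysed by randomized group, alongside the FAS analysis.
2. If an as-treated analysis is kept, make it symmetric and supplementary. Define exposure as a stent placed during the index thrombectomy, yes or no, and apply it in both directions. Say that deferred stenting in a control is part of the allocated strategy and does not count as crossover.

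The cost is about two sentences and no new data collection. The current rule already needs the randomized group for every unstented patient, so allocation must in any case be kept with the anonymized safety records.
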